9.8. Urgent Safety Measures

All arrangements described in this section apply only to the extent that protocol requirements cannot be met because of restrictions due to a crisis, such as the COVID-19 pandemic. Study center visits should take place to the extent possible and usual protocol requirements adopted for all subjects as soon as the crisis-related limitations permit.

Exceptional measures taken in response to a crisis (e.g., COVID-19) and their impact on study results, such as tests done in a local laboratory, will be explained, assessed and reported in the clinical study report following ICH E3 guidance.

In case any visit described in the Schedule of Activities (Table 2) cannot be conducted at the study center within the visit window due to restrictions related to COVID-19 or another such crisis, a telephone visit, home visit and/or video (central rater) call should be arranged.

The telephone visit should include all protocol assessments that can be performed remotely and should take place within the original visit window. The decision to replace the site visit with an alternate contact method will be made on a case by case basis with the Study Sponsor.

In addition to the remote visit, the Investigator should make reasonable efforts to complete the following assessments/procedures as soon as possible (if applicable to the study visit):

- Concomitant medication review/collection
- Vital signs (blood pressure, heart rate, respiration rate, temperature)
- 12-lead safety ECG
- Adverse event collection
- Chemistry and hematology
- Urine drug screening
- Urine pregnancy test (if applicable)
- HAM-A (central rater)
- C-SSRS SLV Version

9.9. Special Situations

Special situations with study drug are defined as the following:

- Medication error or incorrect drug administration
- Overdose (exceeds the protocol-specified maximum; see Section 9.5 for the definition of overdose)
- Deliberate abuse
- Deliberate misuse
- Drug interaction
- Occupational exposure

Clinical Study Protocol: MMED008

- Breastfeeding with suspected infant exposure
- Drug accountability issue (e.g., diversion) if linked to an AE (see Section 6.7)

If any of these special situations with study drug occur, they will be reported on the special situations with study drug eCRF page, even if there is no accompanying AE. All clinical manifestations in relation to these special situations (as defined above) will be reported as an SAEs or AESIs at the same time using the corresponding section of the eCRF.

For example, if a medication error or interaction occurred, the Investigator will assess whether to consider an AE to have occurred, and if so, will assign the possible relationship to the study drug.

Additional information may be requested by the site including all AE information and all triggering drug accountability discrepancies.

9.10. Reporting of Pregnancy to the Sponsor

For all WOCBP, urine dipstick pregnancy testing will be done locally as described in Section 8.3.4 and outlined in the Schedule of Activities (Table 2). If any subject becomes pregnant prior to Day 1/Randomization (Visit 3A), the subject is not eligible to be randomized in the study.

As this is a single-dose study, if a subject becomes pregnant during the study after Day 1/Dosing Session (Visit 3B), she is not required to withdraw from the study.

If a female sexual partner of a male subject becomes pregnant (by the male subject) within 28 days after Day 1/Dosing Session (Visit 3B), and if the subject agrees, the subject's pregnant partner should be notified and requested to sign a Release of Information form, permitting transfer of information regarding the pregnancy and outcome to the Sponsor.

The Investigator must inform the subject of their right to receive treatment information. If the pregnant subject (or pregnant female partner of the subject) chooses to receive unblinded treatment information, the individual blind should be broken, and the treatment assignment provided to the subject's partner. The study team will remain blinded to the subject's (partner's) treatment assignment. If she agrees, the Investigator should notify the subject's (partner's) primary care physician of the pregnancy and provide details of the subject's participation in the study and treatment (blinded or unblinded, as applicable).

Pregnancy is to be reported to the Sponsor within 24 hours of awareness by the study site personnel, using the pregnancy reporting forms and the contact information in Section 9.4.2. The expected date of delivery or expected date of the end of the pregnancy, last menstruation, estimated conception date, pregnancy result, neonatal data, etc. should be included in this information, as available.

The Investigator will follow the medical status of the mother, as well as the fetus, and will report the outcome to the Sponsor.

Clinical Study Protocol: MMED008

10. STATISTICAL CONSIDERATIONS

Statistical analysis will be done by the Sponsor or under the authority of the Sponsor.

A general description of the statistical methods to be used to analyze the efficacy and safety data is outlined below. Specific details will be provided in the MMED008 Statistical Analysis Plan (SAP) that will be finalized prior to unblinding of the study. The treatment code will be opened after the study database has been locked.

This study will utilize the Multiple Comparison Procedure-Modelling (MCP-Mod) approach to analyze the primary outcome measure. The MCP-Mod is a hybrid approach that combines hypothesis testing and modeling in a structured manner to analyze Phase 2 dose-ranging studies to find suitable dose(s) for confirmatory Phase 3 trials.

10.1. Analysis Sets

The following analysis sets will be defined for the statistical analysis. Subjects without valid written study informed consent will be excluded from all analysis sets.

Table 8: MMED008 Analysis Sets

Analysis Set	Description
Randomized Set (RAN)	All subjects who received a randomization number, regardless of receiving trial medication. Subjects will be analyzed according to the treatment assigned.
Safety Set (SAF)	All subjects who received the double-blind study drug. Subjects will be analyzed according to actual treatment received.
Full Analysis Set (FAS)	All subjects in RAN with a valid Baseline HAM-A assessment and at least one valid post-baseline HAM-A assessment. Subjects will be analyzed according to the treatment assigned.
Per Protocol Set (PPS)	All subjects in FAS who had no major protocol deviations deemed as impacting the primary endpoint ^a . Subjects will be analyzed according to the actual treatment received.

^a An impact assessment will be performed prior to the unblinding of the study. The impact assessment will determine whether a major protocol deviation impacts the primary endpoint thereby leading to the removal of the respective subject(s) from the PPS.

10.2. Statistical Analyses

10.2.1. Patient Demographics and Other Baseline Characteristics

Summary statistics will be provided by treatment group for demographics and baseline characteristics, including sex at birth, self-identified gender, age, race, weight, height, BMI, systolic blood pressure, diastolic blood pressure, medical history, baseline values for HAM-A Total Score, PSQI, MADRS, CGI-I, CGI-S, PGI-S and ASEX. These summaries will be performed for the FAS and PPS populations.

Continuous variables will be summarized using n, mean, standard deviation (SD), median, Q1 (25th percentile), Q3 (75th percentile), minimum, and maximum. Categorical variables will be summarized using frequency and percentage.

Clinical Study Protocol: MMED008

10.2.2. Efficacy Analyses

10.2.2.1. Primary Estimand

The primary estimand quantifies the treatment effect of MM-120 at 4 weeks post-dose administration while accounting for intercurrent events (IEs) with potential confounding effects and IEs leading to study discontinuation prior to the 4-week assessment.

The following attributes describe the primary estimand:

- Population: As defined by the Inclusion/Exclusion criteria
- Endpoint: Change from Baseline to Week 4 in HAM-A Total Score
- Treatment of interest /the randomized treatment: 4 doses of MM-120 (25, 50, 100, or 200 µg free-base equivalent) or placebo as a single-dose treatment.
- Handling of IEs prior to HAM-A assessment at Week 4:
 - Intake or change in concomitant medications/therapies which have potential confounding effects per the impact assessment.
 - Intake of prohibited medications/therapies assessed as "Yes" per the impact assessment.
 - *Policy strategy:* Available data recorded after the IE will be set to missing; such missing data will be imputed/substituted under a Missing Not at Random (MNAR) assumption by borrowing information from the placebo arm subjects (reference-based imputation).
 - IEs leading to study discontinuation due to other reasons.
 - IEs related to the COVID-19 pandemic
 Policy strategy: Available data will be used; missing data will be imputed under a Missing at Random (MAR) assumption, borrowing information from subjects in the same treatment arm.
- Summary measure: Identification of the dose-response curve and estimation of the target dose

Statistical Methods & Analysis

The MCP-Mod methodology (Bretz 2005; Pinheiro 2014) will be employed to assess the primary objective: to investigate the dose-response relationship for different doses of MM-120 versus placebo in change from Baseline in HAM-A Total Score at Week 4. An overview of the steps for the MCP-Mod methodology is given below.

Step 1

The analysis to derive the test statistics is based on an analysis of covariance (ANCOVA) model with the change from Baseline to Week 4 for HAM-A Total Score as a response variable, treatment (placebo and all MM-120 doses), and Baseline value of HAM-A Total Score. Centers will be pooled according to country and region as appropriate and as defined in the SAP prior to unblinding.

Missing or potentially biased data will be imputed as described in the following section on Handling of Missing/Potentially Biased Values. To account for the imputation uncertainty, this ANCOVA model will be repeated for each imputed dataset, which results in a set of least-squares (LS) mean estimates for all dose groups and the related covariance matrices. Rubin's rule will be used to combine the multiple sets of LS mean estimates and the related covariance matrices to a single set of LS mean estimates of change from Baseline to Week 4 for HAM-A Total Score for all dose groups and the related covariance matrix.

[figure not shown]
A range of possible dose-response relationships will be considered to take model uncertainty into account (see Figure 2). The following six candidate dose-response curves will be used to derive the optimal model contrasts for the multiple contrast tests:

- Sigmoid Emax (ED50, hill):
 - -10, 1
 - -100, 5
 - -100, 10
 - -150, 10
- Emax (D50 = 100)
- Linear

The optimal contrasts derived from the candidate model sets will be applied to the combined estimated dose means and covariance matrix to obtain the t-statistics for each candidate model and the common critical value $C_{0.05}$ derived from the reference multivariate t-distribution with the 6x6 correlation matrix induced by testing the candidate dose-range models with respect to comparing all MM-120 doses to the placebo group.

The null hypothesis will be rejected and the statistical significance of dose-response in change from Baseline to Week 4 for HAM-A Total Score will be established if the max $(t_1, t_2, t_3, ..., t_6) \ge C_{0.05}$.

Figure 2: Candidate Dose-response Curves

Step 2

The response data in each imputed data set, including relevant covariates, will be used to fit the models in the candidate set. The estimated dose-response will be derived by using model averaging methods on a subset of candidate models, for which the associated contrast tests are statistically significant. The ≤ 3 models with the largest t-statistics $\geq C_{0.05}$ as calculated above will be selected as the basis for the model averaging.

Model averaging will be carried out for each imputed data set, and the resulting mean efficacy estimates, and confidence intervals will be derived using the combination variance that accounts for the uncertainty of the imputed data using Rubin's combination rules. Comparisons between MM-120 doses and placebo will be simultaneously derived for the model averaged estimates together with confidence intervals reflecting the imputation procedure applied. The

model-averaging-based estimates of the mean changes from Baseline to Week 4 for HAM-A Total Score within each dose group, and the mean differences between MM-120 and placebo and their confidence intervals will then be displayed.

Target dose selection will be based on the model change from Baseline to Week 4 for HAM-A Total Score over the dose range studied.

Detailed information about the algorithms including multiple imputation will be specified in the SAP that will be finalized prior to unblinding.

The MCP-Mod analysis will be performed on the FAS population. It will also be performed on the PPS as a sensitivity analysis.

Handling of Missing/Potentially Biased Values

Missing data will be imputed using a multiple imputation approach assuming that the missingness mechanism can be retrieved from observed data. The imputation model will include the longitudinal sequence of HAM-A Total Score.

For IEs, handling will depend on the IE causing the missing or potentially biased value as follows:

- The data recorded after the IE will be imputed/substituted under an MNAR assumption by borrowing information from the placebo arm subjects (reference-based imputation) for the following:
 - For intake or change in concomitant medications/therapies that have potential confounding effects per the impact assessment; or
 - For intake of prohibited medications/therapies assessed as "Yes" per the impact assessment.
- Missing data will be imputed under a MAR assumption, borrowing information from subjects in the same treatment arm for the following:
 - For IEs leading to study discontinuation due to other reasons than the above, including IEs related to the COVID-19 pandemic.

Centers will be pooled according to country and region as appropriate and as defined in the SAP prior to unblinding.

The full detailed information about the multiple imputation algorithms will be specified in the SAP.

10.2.2.2. Sample Size Determination

A total sample of 180 subjects (36 per dose arm and 36 for the placebo arm) is required to ensure a mean power >87% for an MCP-Mod Analysis rejecting the hypothesis of a constant dose-response curve using the multiple comparisons procedure (MCP), assuming a null placebo response, a maximum standardized effect of 0.6 within the doses range, and a common

standard deviation within the dose arms, if a study-wise one-sided type-1 error rate < 0.05 is required.

The analysis assumes 4 doses of active medication (25, 50, 100, and 200 µg freebase-equivalent) and placebo. The required sample size for each dose arm is 36 subjects.

The R package Dose Finding (https://CRAN.R-project.org/package=DoseFinding) has been used to estimate the sample size and the corresponding power. The power for each model is estimated as shown in Table 9.

Table 9: Study MMED008 Power by Model

Model	Power (%)	
Sigmoid Emax (ED50, hill)		
10, 1	84.5	
100, 5	90.7	
100, 10	91.0	
150, 10	89.9	
Emax (D50 = 100)	83.2	
Linear	85.0	

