Outcome Measures	Change in HAM-A Total Score from Baseline to Week 4					
	Key Secondary Endpoint					
	Change in HAM-A Total Score from Baseline to Week 8					

Secondary Endpoints

- Change in HAM-A Total Score from Baseline to End of Study
- Change from Baseline to Week 1, Week 2 (where applicable), Week 4, Week 8, and End of Study in score for the following measures:
 - Montgomery-Åsberg Depression Rating Scale (MADRS)
 - Clinical Global Impression Severity (CGI-S) Scale
 - o Clinical Global Impression Improvement (CGI-I) Scale
 - o Patient Global Impression Severity (PGI-S) Scale
 - o Patient Global Impression Change (PGI-C) Scale
 - Sheehan Disability Scale (SDS)
 - o EuroQol-5 Dimentions-5 Levels (EQ-5D-5L)
 - Pittsburgh Sleep Quality Index (PSQI)
 - Arizona Sexual Experiences Questionnaire (ASEX)

Safety Endpoints

Safety will be evaluated based on the following measure/assessments:

- Adverse events
- Vital signs (heart rate, blood pressure, respiration rate, temperature)
- 12-lead safety ECG
- Physical examination
- C-SSRS
- Safety laboratory evaluation

Statistical Methods

This study will utilize the Multiple Comparison Procedure-Modelling (MCP-Mod) approach to analyze the primary outcome measure (Bretz 2005, Pinheiro 2014). The MCP-Mod is a hybrid approach that combines hypothesis testing and modeling in a structured manner to analyze Phase 2 dose-finding studies to find suitable dose(s) for confirmatory Phase 3 trials. A total sample of 180 subjects (36 per dose arm and 36 for the placebo arm) is required to ensure a mean power > 87% for an MCP-Mod analysis rejecting the hypothesis of a constant dose-response curve using the multiple comparisons procedure (MCP), assuming a null placebo response, a maximum standardized effect of 0.6 within the dose range, and a common standard deviation within the dose arms, if a study-wise one-sided type-1 error rate < 0.05 is required. The analysis assumes 4 doses of active medication (MM-120 25, 50, 100, and 200 μg freebase-equivalent) and placebo.

Schedule of Activities

Table 2: MMED008 Schedule of Activities

STUDY PERIOD	Optional Prescreen	SCREENING	BASELINE & DOSING			FOLLOW-UP					
Visit	Prescreen	Screening ^a	Baseline	Randomiz	ay 1 ation (3A) & ession (3B)	Day 2	Week 1	Week 2	Week 4	Week 8	Week 12 (or Early WD)/EOS
Visit Number	N/A	1	2	3A	3B	4	5	6	7	8	9

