4.2. Number of Subjects

The target sample size for this study is approximately 180 subjects.

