## 4.2 Analysis Sets

The following populations will be defined for the purpose of analysis:

- Randomized Set (RAN) all subjects who received a randomization number, regardless of receiving study drug. Subjects will be analyzed according to the treatment assigned.
- Safety Set (SAF) all subjects who received the double-blind study drug. Subjects will be analyzed according to the actual treatment received.
- Full Analysis Set (FAS) all randomized subjects with a valid baseline HAM-A assessment and at least one valid post-baseline HAM-A assessment. Subjects will be analyzed according to the treatment assigned.
- Per Protocol Set (PPS) All subjects in the full analysis set who had no major protocol deviations deemed as impacting the primary endpoint. Subjects will be analyzed according to the actual treatment received.

An impact assessment will be performed prior to the unblinding of the study. The impact assessment will determine whether a major protocol deviation impacts the primary endpoint thereby leading to the removal of the respective subject(s) from the PPS.

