## 6.1.1 Handling of Missing Data and Potentially Biased Values

Missing data for the primary endpoint will be imputed using a multiple imputation approach assuming that the missingness mechanism can be retrieved from observed data. The imputation model will include the treatment group and the longitudinal sequence of HAM-A Total Score. Imputations will be performed 20 times using SAS PROC MI with the fully conditional specification (FCS) method.

For intercurrent events (IEs) the following methods will be used:

- The data recorded after the IE will be set to missing and imputed under a Missing Not at Random (MNAR) assumption by borrowing information from the placebo arm subjects (reference-based imputation) for the following:
  - Concomitant/prohibited medications that meet the threshold for impact = "Yes" during the impact assessment will be considered as the IE. Any observations after such an IE will be set to missing and will be imputed using the MNAR assumption.
- Available data will be used; missing data will be imputed under a Missing at Random (MAR) assumption, borrowing information from subjects in the same treatment arm for the following:
  - For IEs leading to study discontinuation due to other reasons
  - IEs related to the COVID-19 pandemic.

For missing data not due to IEs the imputation will be performed based on MAR assumption.

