## Step 1

A test statistic will be derived from the data using an analysis of covariance (ANCOVA) model with change from Baseline to Week 4 for the HAM-A Total Score as a response variable, treatment arm and Baseline value of HAM-A Total Score as covariates. Geographic region will be included as a covariate if clinical sites outside the US are used; otherwise, it will not be included in the model. Missing or potentially biased values occurring after IEs will be imputed as described in Section 6.1.1.

The ANCOVA model will be repeated for each imputed dataset, which results in a set of least squares (LS) mean estimates for all dose groups and the related covariance matrices. Rubin's rule will be used to combine the multiple sets of LS mean estimates and the related covariance matrices to a single set of LS mean estimates of change from Baseline to Week 4 for HAM-A Total Score for all dose groups and the related covariance matrix. The SAS procedure PROC MIANALYZE will be used to combine the results from imputed datasets and provide valid statistical inferences.

A range of possible dose-response relationships will be considered to take model uncertainty into account. The following six candidate dose-response curves, as depicted below in Figure 1, will be used to derive the optimal model contrasts for the multiple contrast tests:

- Sigmoid Emax (ED50, hill):
  - o 10, 1
  - o 100, 5
  - o 100, 10
  - o 150, 10
- Emax (D50 = 100)
- Linear

The optimal contrasts derived from the candidate model sets will be applied to the combined estimated dose means and covariance matrix to obtain the t-statistics for each candidate model and the common critical value  $C_{0.05}$  derived from the reference multivariate t-distribution with the 6x6 correlation matrix induced by testing the candidate dose-range models with respect to comparing all MM-120 doses to the placebo group.

The null hypothesis will be rejected and the statistical significance of dose-response in change from Baseline to Week 4 for HAM-A Total Score will be established if the max ( $t_1$ ,  $t_2$ ,  $t_3$ ,  $t_4$ ,  $t_5$ ,  $t_6$ )  $\ge C_{0.05}$ .

Mind Medicine, Inc. MMED008 Statistical Analysis Plan (Final version 1.0)

## Step 2

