## 9 SAMPLE SIZE AND POWER CALCULATIONS

A total sample of 180 subjects, 36 per arm, is required to ensure a mean power >87% for an MCP-Mod Analysis rejecting the hypothesis of a constant dose-response curve using the multiple comparisons procedure (MCP), assuming a null placebo response, a maximum standardized effect of 0.6 within the doses range, and a common standard deviation within the dose arms, if a studywise one-sided type-1 error rate <0.05 is required.

The analysis assumes 4 doses of active medication (25, 50, 100 and 200  $\mu$ g freebase-equivalent) and placebo. The required sample size for each arm is 36 subjects.

The R package Dose Finding (https://CRAN.R-project.org/package=DoseFinding) has been used to estimate the sample size and corresponding power. The power for each model is estimated as shown Table 6.

Table 6	Power by Mode

Model	Power (%)
Sigmoid Emax (ED50, hill)	
10, 1	84.5
100, 5	90.7
100, 10	91.0
150, 10	89.9
Emax (D50 = 100)	83.2
Linear	85.0

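### Does the >87% mean power fail because it takes all 180 enrolled subjects as complete cases?

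*Protocol*

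**What the plan says.** The Protocol Synopsis says that 180 subjects "is required to ensure a mean power > 87% for an MCP-Mod analysis". Protocol 10.2.2.2 repeats this for the same total: "36 per dose arm and 36 for the placebo arm) is required to ensure a mean power >87% for an MCP-Mod Analysis". SAP 9 adds: "The required sample size for each arm is 36 subjects". The conditions are listed in the same sentence: no placebo response, a maximum standardized effect of 0.6 within the dose range, a common SD across arms, and a one-sided study-wise error below 0.05. Table 9 of the Protocol (Table 6 of the SAP) gives the power for each of the six candidate models.

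The enrolment number is the same. Protocol 4.2: "The target sample size for this study is approximately 180 subjects". SAP 8 relies on about 180 subjects giving adequate power and closes enrolment.

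The primary analysis provides for incomplete data:

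- The FAS requires "at least one valid post-baseline HAM-A assessment" (SAP 4.2).
- After an impactful medication event, "such missing data will be imputed/substituted under a Missing Not at Random (MNAR) assumption by borrowing information from the placebo arm subjects" (Protocol 10.2.2.1). SAP 6.1.1 agrees: "Any observations after such an IE will be set to missing and will be imputed using the MNAR assumption".
- Other missing scores are imputed under MAR from the same arm.
- The ANCOVA uses "treatment arm and Baseline value of HAM-A Total Score as covariates" (SAP 6.1.2, Step 1).

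Neither power section gives a missing-data rate, an intercurrent-event rate, an SD in HAM-A points, or whether 0.6 is on the raw or the baseline-adjusted SD.

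**The concern.** The number needed and the number enrolled are identical, and the margin over 87% is small. Losing the information of one subject per arm takes the mean to 86.5%. The estimand names events that remove or replace Week 4 scores, and placebo-based imputation pulls an active arm towards placebo. A reader may conclude that 87% describes 180 complete cases rather than 180 enrolled subjects under the planned analysis, and that the trial has less power than claimed. If that were so, the sample size justification would be overstated in the Synopsis, Protocol 10.2.2.2 and SAP 9, and SAP 8 would rest on it.

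**Working it through.** **Inputs.** From Protocol 10.2.2.1, 10.2.2.2 and SAP 9: doses 0, 25, 50, 100 and 200 µg; 36 per arm; the six candidate shapes; maximum effect 0.6 SD within the dose range; one-sided 0.05. All loss rates, event rates and correlations below are assumptions, because the documents give none.

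**Step 1: reproduce Table 9.** For each shape with model mean vector m, the optimal contrast at equal n is proportional to m minus its average. The critical value C comes from the six-dimensional multivariate t with 5 × 36 − 5 = 175 df and is about 2.045. Power is P(max t ≥ C) under each shape, by simulation.

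| Model | Table 9 (%) | Recomputed (%) |
|---|---|---|
| Sigmoid Emax 10, 1 | 84.5 | 84.5 |
| Sigmoid Emax 100, 5 | 90.7 | 90.7 |
| Sigmoid Emax 100, 10 | 91.0 | 91.0 |
| Sigmoid Emax 150, 10 | 89.9 | 89.9 |
| Emax 100 | 83.2 | 83.2 |
| Linear | 85.0 | 85.0 |

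The mean of Table 9 is 524.3 / 6 = 87.4%. The table is correct, and it is a complete-data calculation at 36 per arm.

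**Step 2: what could lower it.** These cases assume that 0.6 is on the SD used in the analysis and that loss is equal across arms.

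- *Loss with no recovery:* n = 36(1 − m), where m is the fraction missing.
- *Partial recovery:* if earlier HAM-A scores explain half the Week 4 variance (R² = 0.5), effective n = 36 / (1 + 0.5·m/(1 − m)).

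| Loss m | n, no recovery | Mean (lowest) power | Effective n, R² = 0.5 | Mean (lowest) power |
|---|---|---|---|---|
| 5% | 34.2 | 85.8 (81.4) | 35.08 | 86.6 (82.3) |
| 10% | 32.4 | 84.0 (79.5) | 34.11 | 85.7 (81.3) |
| 15% | 30.6 | 82.1 (77.4) | 33.08 | 84.7 (80.2) |

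- *Placebo-based imputation alone:* if a fraction q of each active arm is shifted fully to the placebo mean, the effect is 0.6(1 − q). For q = 2% it is 0.588 and the mean is 86.2%. For q = 5% it is 0.57 and the mean is 84.2%. This applies only if 0.6 is the effect before that dilution.
- *Both together:* 10% loss with 5% diluted gives 80.5%.
- *Unequal loss:* the table above is not a lower bound. Nine subjects (5% of 180) all lost from the 200 µg arm give 82.4%.

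**Step 3: what could raise it.** If 0.6 is on the raw SD of change, the ANCOVA works on a smaller SD. With r the correlation between baseline and change, the effect becomes 0.6 / √(1 − r²).

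| r | Effect | Loss, no recovery | Mean power |
|---|---|---|---|
| 0.30 | 0.6/√0.91 = 0.629 | none | 90.0 |
| 0.20 | 0.6/√0.96 = 0.612 | 5% | 87.0 |
| 0.30 | 0.629 | 10% | 87.0 |
| 0.38 | 0.6/√0.8556 = 0.649 | 15% | 87.1 |

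**Step 4: compare.** Steps 2 and 3 move the figure in opposite directions by similar amounts. The documents fix neither the loss rates nor the SD basis, so they do not settle which side of 87% the enrolled-n power falls on.

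**The case for a change.** The strongest case for a change is that the plan itself foresees these losses. Subjects are tapered off anxiolytics and antidepressants before Baseline, so some may restart them and have later scores replaced from placebo. Imputation does not restore full information: Rubin's rules carry the added uncertainty into the covariance matrix. Subjects with no post-baseline HAM-A leave the FAS altogether. A sentence labelling the 87% as complete-data power and naming the SD would cost almost nothing.

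The omission stands: complete data is an unlisted assumption, and the SD basis is not given. What does not follow is that the claim is wrong. The power sentence is conditional on listed assumptions and is correct under them. Phrasing in terms of a common SD within the arms can fairly be read as the ordinary within-arm SD, in which case the calculation leaves out the gain from baseline adjustment and is conservative.

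The design also limits missing Week 4 scores. There is one witnessed dose, so there is no drug discontinuation. Early withdrawals are asked to complete the final-visit assessments, which include HAM-A. SAP 4.3 accepts any score from Day 22 to Day 43 as Week 4, including unscheduled visits. None of this supplies a rate, but it makes 10% to 15% an illustration rather than an expectation.

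**Conclusion.** The concern describes a real gap in reporting, not a fault in the plan. Table 9 and the mean above 87% are right for 36 complete Week 4 observations per arm under the stated conditions. For 180 enrolled, illustrative equal losses of 5% to 15% lower the mean by about 1 to 5 points if 0.6 is on the adjusted SD. If 0.6 is on the raw SD, baseline-change correlations of 0.20 to 0.38 bring it back to about 87%. Larger falls need unequal loss, or loss and placebo-based dilution together; nothing in the documents points to either at a particular rate.

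A margin of 0.4 point on an approximate enrolment number and an assumed effect has no bearing on any decision, and the lowest model power, 83.2%, is already printed. Writing the assumptions down would leave enrolment, the contrast test, the imputation, the estimates and the statement of adequate power unchanged. No change follows.
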